## 11.6. Appendix 6: Reporting Standards for Missing Data

### 11.6.1. Premature Withdrawals

Element	Reporting Detail
General	
 
Subjects will receive mepolizumab 100 mg SC every for weeks, but it is expected that subjects would withdraw before the Exist Visit due to NUCALA becoming commercially available before the end of the study. Thus, this study will not have any completers and all subjects will eventually withdraw (See Section 2.3).
 
Withdrawn subjects will not replaced in the study.
 
All available data from subjects who were withdrawn from the study will be listed and all available planned data up to and including the date of early withdrawal will be included in summary tables and figures, unless otherwise specified.
 

	
 
Early withdrawal visits will be slotted as per Appendix 2: Assessment Windows.
 

Screen Failures	
 
For the purposes of this study screen failures will be defined as follows:
 
Subjects will be assigned a study number at the time of signing the informed consent (Baseline Visit).
 
Those subjects that complete at least one Visit 1 (Baseline Visit) procedure but do not subsequently receive study treatment will be designated as screen failures.
 

### 11.6.2. Handling of Missing Data

Element	Reporting Detail
General	• Missing data occurs when any requested data is not provided, leading to blank fields on the collection instrument:
	
 
These data will be indicated by the use of a "blank" in subject listing displays. Unless all data for a specific visit are missing in which case the data is excluded from the listing.
 

	
 
Answers such as "Not applicable" and "Not evaluable" are not considered to be missing data and should be displayed.
 

	
 
Results which are found to be below the limit of quantification (BLQ) are not missing data and will be included in all displays. See Section 11.5.4 for the handling of this data.
 

	• The ACQ-5 score will be considered as missing if <4 items of the questionnaire are completed at a visit. ACQ-5 Responder/Non-responder category will be missing if the overall ACQ-5 score is missing.
	
 
If a blood eosinophil count of zero is reported, it will be imputed with half of the lowest possible blood eosinophil count, where applicable, prior to log transforming the data (Note: this imputation has typically been 0.5 * 0.01 GI/L = 0.005 GI/L for previous mepolizumab studies).
 

	
 
Missing values will not be imputed for any of the other endpoints.
 

Outliers	• Any subjects excluded from the summaries and/or statistical analyses will be documented along with the reason for exclusion in the clinical study report.

### 11.6.2.1. Handling of Missing and Partial Dates

Element	Reporting Detail
General	• The eCRF allows for the possibility of missing or partial dates (i.e., only month and year is captured) to be recorded for event start and end dates.
	• The recorded missing or partial date will be displayed in listings as captured.
Concomitant Medications	• Partial dates for any concomitant medications recorded in the CRF will be imputed using the following convention:
	
 
If the partial date is a start date, a '01' will be used for the day and 'Jan' will be used for the month
 

	
 
If the partial date is a stop date, a '28/29/30/31' will be used for the day (dependent on the month and year) and 'Dec' will be used for the month.
 

Adverse Events, Exacerbations	• Any partial dates for adverse events and exacerbations will be raised to data management. If the full date cannot be ascertained, the following assumptions will be made:
	
 
If the partial date is a start date, a '01' will be used for the day and 'Jan' will be used for the month.
 

	
 
However, if these result in a date prior to the start of treatment and the event could possibly have occurred during treatment from the partial
 

	information, then the study treatment start date will be assumed to be the start date and hence the event is considered On-treatment (worst case),

Element	Reporting Detail
	as per Appendix 3: Treatment Phases.
	(dependent on the month and year) and 'Dec' will be used for the month.
	• The above listed imputations will also be applied when calculating the time to onset and the duration of the event containing missing or partial start and end dates.
	
 
Start or end dates which are completely missing (i.e. no year specified) will remain missing, with no imputation applied. Consequently, time to onset and duration of such events will be missing.
 

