#### Exacerbations

An exacerbation of asthma as defined as:

Worsening of asthma which requires use of systemic corticosteroids and/or hospitalisation and/or Emergency Department (ED) visits.

- For all subjects, i.v. or oral steroid (e.g., prednisone) for at least 3 days or a single IM CS dose is required. For subjects on maintenance systemic corticosteroids, at least double the existing maintenance dose for at least 3 days is required.
- Within each subject, exacerbations that occurred less than seven days apart will be collapsed into a single exacerbation. Exacerbations for which the collapsing has already been performed

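### The partial-date rule in SAP 11.6.2.1 sets the month to Jan or Dec without limiting this to dates whose month is missing, so followed literally it discards a recorded month

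*SAP*

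**What the plan says.** SAP 11.6.2.1 opens by saying that the eCRF allows missing or "partial dates (i.e., only month and year is captured) to be recorded for event start and end dates". For adverse events and exacerbations it then gives these steps:

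- Query first: "Any partial dates for adverse events and exacerbations will be raised to data management".
- If the full date cannot be recovered, then for a start date "a '01' will be used for the day and 'Jan' will be used for the month".
- For a stop date the day is 28, 29, 30 or 31 ("dependent on the month and year) and 'Dec' will be used for the month"). Part of this bullet is lost in the extracted text for adverse events and exacerbations. What survives matches the complete bullet in the concomitant-medication row, so I read the two as the same rule.
- If the imputed start precedes first dose but the event could have arisen on treatment, "then the study treatment start date will be assumed to be the start date".
- "Start or end dates which are completely missing (i.e. no year specified) will remain missing, with no imputation applied".

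The section also applies these imputations to time to onset and duration.

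Two other parts of the SAP matter. In the Exacerbations derivation of 11.5.3, "exacerbations that occurred less than seven days apart will be collapsed into a single exacerbation". Under 8.1.4 and 8.1.5.1 the primary analysis is a negative binomial model of on-treatment exacerbations with log time on treatment as offset.

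**The concern.** The section describes a partial date as one whose month is known and then tells the programmer to replace the month. The day list for stop dates makes sense only if a recorded month is kept, because December always has 31 days. The rule therefore conflicts with both its own definition and its own stop-day wording.

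If the literal wording is programmed, onset times and durations are wrong for every event still partial after query, including those in the time-to-onset rows of the special-interest profiles (SAP 7.3). Treatment phase can also be wrong. For the primary endpoint, a widened exacerbation can swallow its neighbours if the collapse uses the imputed dates. The offset does not change when events merge, so only the numerator falls. The study has one arm and no hypothesis test, so the estimated rate and its interval are the primary efficacy result.

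**Working it through.** The plan has no figure to reproduce: Protocol 8.2.1 gives no sample size calculation, and neither document gives an expected exacerbation rate or a frequency of partial dates. I applied the SAP rules to worked cases and then to simulated data. Dates in the cases are illustrative.

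**Case 1: onset.** First dose 16 Mar 2015, adverse event recorded as Nov 2015.
- Literal rule: start = 1 Jan 2015. This is before first dose, but the event could be on treatment, so the start is reset to 16 Mar 2015. SAP 11.3.2.1 gives onset = onset date − first dose + 1 = day 1.
- Month kept: start = 1 Nov 2015, which is 230 days after first dose, so onset = day 231.

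**Case 2: collapse.** One subject with true exacerbations 4–14 Mar, 10–20 Jun and 2–12 Oct 2016, the June event being partial. The collapse is assumed to run on imputed dates.

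| Partial in June event | Literal: span, count | Month kept: span, count |
|---|---|---|
| Start and stop | 1 Jan–31 Dec, 366 days, 1 | 1–30 Jun, 30 days, 3 |
| Start only | 1 Jan–20 Jun, 172 days, 2 | 1–20 Jun, 20 days, 3 |
| Stop only | 10 Jun–31 Dec, 205 days, 2 | 10–30 Jun, 21 days, 3 |

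An event crossing New Year (Dec 2015 to Jan 2016, first dose before 2015) spans 365 + 366 = 731 days under the literal rule. A partial event with no neighbour still counts as 1.

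**Case 3: phase.** On-treatment phase ends 30 Sep 2016; an exacerbation has its start recorded as Nov 2016. The literal rule dates it 1 Jan 2016, so it becomes on-treatment and adds 1 to the count unless it merges. With the month kept it starts 1 Nov 2016 and stays post-treatment. For adverse events, SAP 11.3.2 lets contrary evidence from the recorded month and year override the on-treatment default, which may prevent this. The efficacy phases in 11.3.1 have no such clause.

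**Simulation.** From the documents: 375 subjects (Protocol 4.1), the 172-week maximum, the imputation with its reset, and the under-7-day collapse. Assumed: follow-up of 52 to 172 weeks, gamma dispersion 1, events of about 10 days, both dates partial in affected events, no post-treatment events, and 20 replicates per setting. Change in rate = rate under rule / rate with true dates − 1.

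| Assumed rate/year | % partial | True | Literal | Month kept | Literal change | Month-kept change |
|---|---|---|---|---|---|---|
| 0.5 | 1 | 0.474 | 0.470 | 0.473 | −0.8% | −0.2% |
| 0.5 | 5 | 0.488 | 0.473 | 0.487 | −3.1% | −0.2% |
| 0.5 | 10 | 0.479 | 0.445 | 0.475 | −7.1% | −0.8% |
| 1.0 | 1 | 0.927 | 0.916 | 0.926 | −1.2% | −0.1% |
| 1.0 | 5 | 0.889 | 0.829 | 0.883 | −6.7% | −0.7% |
| 1.0 | 10 | 0.919 | 0.799 | 0.905 | −13.1% | −1.5% |
| 2.0 | 1 | 1.685 | 1.646 | 1.681 | −2.3% | −0.2% |
| 2.0 | 5 | 1.667 | 1.482 | 1.645 | −11.1% | −1.3% |
| 2.0 | 10 | 1.667 | 1.324 | 1.626 | −20.6% | −2.5% |

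A separate simulation (0.7 per year, dispersion 1, 1.2 to 3.3 years each, events of 5 to 15 days) agrees. At 1% partial the mean count falls from 556.6 to 550.7, or 5.9/556.6 = 1.1%; with the month kept it is 556.1, a fall of 0.5/556.6 = 0.1%.

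**The case against.** The strongest reply is that the literal reading is not the intended one. The stop day varies with the month, and a date counts as completely missing only when the year is absent, so year-only dates must also be partial; Jan and Dec fit those. SAP 11.3.2, 11.3.3 and 11.5.4 also use the recorded month where there is one. A careful programmer would probably keep it, and the effect would then be negligible. This is fair evidence of intent, but no section states the limit, and the literal instruction remains.

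It also stands that imputation follows a failed query, that exacerbations are reviewed at every 4-weekly visit, and that a merge needs another exacerbation of the same subject in or near the widened window. The SAP does not say that the collapse uses imputed dates. A gap cannot be computed without completing the date, and 11.5.3 builds collapsed records from analysis start and end dates, so it is the natural reading, but it is an inference.

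A reader might go further in three ways that the documents do not support:

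- That the error always lowers the rate. Case 3 and the reset to first dose can each add on-treatment events.
- That the oral corticosteroid summary (Table 3.12) is distorted. The SAP does not show how medication dates feed that dose.
- That the collapse should use recorded dates only. That could count true continuations twice and depart from a rule which Protocol 6.2.1.1 keeps for consistency across the program.

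**Conclusion.** The contradiction is real and no other section corrects it. For any adverse event or exacerbation still partial after query, the literal rule gives a wrong onset and duration and may give a wrong treatment phase. Its effect on the primary count is conditional on the collapse using imputed dates and on a neighbouring exacerbation, and is usually but not always downward.

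The size is unknown and probably small. With 1% of events partial, the literal rule lowers the simulated rate by 0.8% to 2.3% for assumed rates of 0.5 to 2.0 per year. Keeping the month leaves 0.1% to 0.2%. The losses at 5% and 10% partial show how the effect scales; they are not forecasts. The simulations leave out post-treatment events, so they omit the upward route in Case 3.

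**What to change.** State once in the general row of SAP 11.6.2.1, so that it covers adverse events, exacerbations and concomitant medications, that only the missing component of a date is imputed and that a recorded month and year are always kept. For a known month, the start day is 01 and the stop day is the last day of that month. Jan or Dec is used only when the month itself is missing. Apply the reset to treatment start only after this step.

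The cost is a sentence or two and a check of the date-imputation code. It needs no new data and leaves the collapse rule unchanged. Year-only dates would still span up to a calendar year; this change does not address them.

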### 11.7. Appendix 7: Values of Potential Clinical Importance

### 11.7.1. Laboratory Values

Haematology					
Laboratory Parameter	Units	Category	Clinical Concern Range		
			Low Flag (< x)	High Flag (>x)	
Hematocrit	Ratio of 1	Aged 12+	0.201	0.599	
Haemoglobin	g/L	Aged 12+	71	199	
Platelet Count	x10  / L	Aged 1+	31	1499	
While Blood Cell Count (WBC)	x10  / L	Aged 12+	1.1	-	

Clinical Chemistry					
Laboratory Parameter	Units	Category	Clinical Concern Range		
			Low Flag (< x)	High Flag (>x)	
Calcium	mmol/L	Aged 3+	1.50	3.24	
Glucose	mmol/L	Aged 1+	2.2	27.8	
Phosphorus	mmol/L	Aged 3+	0.32	-	
Potassium	mmol/L	Aged 3+	2.8	6.5	
Sodium	mmol/L	Aged 0+	120	160	

Liver Function			
Test Analyte	Units	Category	Clinical Concern Range
ALT/SGPT	U/L	Aged 3-12	>143 (and Total Bilirubin > 43)
ALT/SGPT	U/L	Aged 13+	>239 (and Total Bilirubin > 43)

# 11.8. Appendix 8: Model Checking and Diagnostics for Statistical Analyses

### 11.8.1. Statistical Analysis Assumptions

En	Endpoint(s) • Frequency of asthma exacerbations during the treatment period		
Analysis		Negative binomial regression analysis	
•	In the event that this model fails to converge, the model will be reviewed and alternatives explored.		
•	Distributional assumptions underlying the model used for analysis will be examined by: o assessing if a sufficient number of events occurred.		
•	If there ar	e any important departures from the distributional assumptions, transformations of	

covariates may be considered or alternative models may be explored as supporting analyses.

### 11.9. Appendix 9: Abbreviations & Trade Marks

### 11.9.1. Abbreviations

Abbreviation	Description
ACQ	Asthma Control Questionnaire
ADA	Anti-drug Antibody
ADaM	Analysis Data Model
AE	Adverse Event
AESI	Adverse Event of Special Interest
ALT	Alanine Transaminase
ASE	All Subjects Enrolled
AT	As Treated
ATC	Anatomical Therapeutic Chemical
BLQ	Below Limit of Quantification
BMI	Body Mass Index
AIC	Akaike's Information Criteria
A&R	Analysis and Reporting
CDISC	Clinical Data Interchange Standards Consortium
CEC	Clinical Endpoint Committee
CI	Confidence Interval
CIL	Clinical Investigation Leader
CPMS	Clinical Pharmacology Modelling & Simulation
CS	Corticosteroid
CSR	Clinical Study Report
CTR	Clinical Trial Register
DBF	Database Freeze
DBR	Database Release
DOB	Date of Birth
DP	Decimal Places
ECG	Electrocardiogram
eCRF	Electronic Case Record Form
ED	Emergency Department
EMA	European Medicines Agency
EW	Early Withdrawal
FDA	Food and Drug Administration
FDAAA	Food and Drug Administration Clinical Results Disclosure Requirements
FEV 1	Forced expiratory volume in 1 second
FVC	Forced Vital Capacity
GCSP	Global Clinical Safety and Pharmacovigilance
GSK	GlaxoSmithKline
ICH	International Conference on Harmonization
ICS	Inhaled Corticosteroids
IDSL	Integrated Data Standards Library
IG	Implementation Guide
IM	Intramuscular

Abbreviation	Description
IMMS	International Modules Management System
IP	Investigational Product
IV	Intravenous
LFT	Liver Function Test
LLQ	Lower Limit of Quantification
MedDRA	Medical Dictionary for Regulatory Activities
mg	Milligram
NAb	Neutralising Antibody
OCS	Oral Corticosteroids
PCI	Potential Clinical Importance
PD	Pharmacodynamic
PDMP	Protocol Deviation Management Plan
PK	Pharmacokinetic
PT	Preferred Term
QC	Quality Control
QTcF	Frederica's QT Interval Corrected for Heart Rate
QTcB	Bazett's QT Interval Corrected for Heart Rate
RAMOS	Randomization & Medication Ordering System
RAP	Reporting & Analysis Plan
RTF	Rich Text File
SAC	Statistical Analysis Complete
SAE	Serious Adverse Event
SAS	Statistical Analysis Software
SC	Subcutaneous
SD	Standard Deviation
SDSP	Study Data Standardization Plan
SDTM	Study Data Tabulation Model
SE	Standard Error
SMQ	Standard MedDRA Query
SOC	System Organ Class
SOP	Standard Operation Procedure
SRM	Study Reference Manual
TA	Therapeutic Area
TFL	Tables, Figures & Listings
TST	Therapeutic Standards Team

### 11.9.2. Trademarks

Trademarks of the GlaxoSmithKline Group of Companies	
HARP	

Trademarks not owned by the GlaxoSmithKline Group of Companies

SAS

### 11.10. Appendix 10: List of Data Displays

### 11.10.1. Data Display Numbering

The following numbering will be applied for RAP generated displays:

Section	Tables	Figures	
Study Population	1.1 to 1.17	1.1	
Safety	2.1 to 2.67	2.1 to 2.2	
Efficacy	3.1 to 3.12	3.1	
Pharmacodynamic	4.1 N/A		
Section	Listings		
ICH Listings	1 to 50		

### 11.10.2. Mock Example Shell Referencing

Non IDSL specifications will be referenced as indicated and if required example mock-up displays will be provided on request.

### 11.10.3. Deliverables

Delivery	Description
SAC	Final Statistical Analysis Complete

### 11.10.4. Study Population Tables

Study Population Tables							
No.	Population	IDSL / Example Shell	Title	Programming Notes	Deliverable		
Popula	tions Analysed						
1.1.	ASE	SP1	Summary of Study Populations	IDSL Include All Subjects Enrolled and As Treated Populations	SAC		
Subject	Disposition						
1.2.	ASE	ES6	Summary of Screening Status and Reasons for Screen Failure	Journal Requirements	SAC		
1.3.	ASE	IE2	Summary of Failed Inclusion/Exclusion/Continuation Criteria for Screen Failures		SAC		
1.4.	AT	IE2	Summary of Failed Inclusion/Exclusion/Continuation Criteria for Subjects within the As Treated Population		SAC		
1.5.	AT	NS1	Summary of Number of Subjects by Region, Country and Site	Add in a column for region, add a total for regions and a total for country EudraCT/Clinical Operations	SAC		
1.6.	AT	ES1	Summary of Disposition and Reasons for Study Withdrawal	ICH E3, FDAAA, EudraCT	SAC		
Demog	raphic and Bas	eline Characteris	tics				
1.7.	AT	DM1	Summary of Demographic Characteristics	ICH E3, FDAAA, EudraCT	SAC		
1.8.	ASE	DM11	Summary of Age Ranges	EudraCT, keep rows ≥12-17, ≥18-<64, ≥65-<84, ≥85	SAC		
1.9.	AT	DM5	Summary of Race and Racial Combinations	ICH E3, FDA, FDAAA, EudraCT	SAC		
1.10.	AT	DM6	Summary of Race and Racial Combinations Details	ICH E3, FDA	SAC		
1.11.	AT	SHELL	Summary of Baseline Lung Function Tests	Include FEV1, FVC, FEV/FVC, %Predicted	SAC		

Study F	Study Population Tables							
No.	Population	IDSL / Example Shell	Title	Programming Notes	Deliverable			
Medica	I Conditions							
1.12.	AT	MH4	Summary of Past Medical Conditions	ICH E3	SAC			
1.13.	AT	MH4	Summary of Current Medical Conditions	ICH E3	SAC			
Concor	nitant Medicati	ons						
1.14.	AT	CM1	Summary of Asthma Concomitant Medications Taken During Treatment by Respiratory Medication Class Group	Footnote: Multi-component medications displayed under the respiratory medication class of each component Programming note: Display RMC and ingredient as previous Asthma studies	SAC			
1.15.	AT	CM1	Summary of Asthma Concomitant Medications Taken Post- Treatment by Respiratory Medication Class Group	Footnote: Multi-component medications displayed under the respiratory medication class of each component Programming note: Display RMC and ingredient as previous Asthma studies	SAC			
1.16.	AT	CM1	Summary of Non-Asthma Medications Taken During Treatment	Footnote: Medications may be displayed under more than one ATC classification	SAC			
Protoco	ol Deviation							
1.17.	AT	DV1	Summary of Important Protocol Deviations	ICH E3	SAC			

201312

### 11.10.5. Study Population Figures

Study I	Study Population: Figures							
No.	Population	IDSL / TST ID / Example Shell	Title	Programming Notes	Deliverable			
Subjec	t Disposition							
1.1	AT	SHELL	Time to End of Study	See Study Population Figure 1.1 (MEA117113 'final' reporting effort), but exclude 'Placebo' and Mepo 300mg SC	SAC			

### 11.10.6. Safety Tables

Safety:	Safety: Tables							
No.	Population	IDSL / Example Shell	Title	Programming Notes	Deliverable			
Exposu	re							
2.1.	AT	SHELL	Summary of Exposure to Study Medication	ICH E3 See format of Study Population Table 1.28 (200862 'final' reporting effort).	SAC			
2.2.	AT	SHELL	Summary of Exposure to Study Medication (Therapeutic Coverage) From Studies MEA115588, MEA115575, MEA115661 and 201312	See format of Study Population Table 7.74 (MEA115661 'manuscript1' reporting effort).	SAC			
Advers	e Events (AEs)							
2.3.	AT	SHELL	Overview of Adverse Events		SAC			
2.4.	AT	AE1	Summary of On-Treatment Adverse Events by System Organ Class and Preferred Term	ICH E3	SAC			
2.5.	AT	SHELL	Summary of Exposure Adjusted On-Treatment Adverse Events by System Organ Class and Preferred Term		SAC			

Safety:	Safety: Tables							
No.	Population	IDSL / Example Shell	Title	Programming Notes	Deliverable			
2.6.	AT	AE5	Summary of On-Treatment Adverse Events by Maximum Intensity by System Organ Class and Preferred Term	ICH E3 Add a Total column across all severities	SAC			
2.7.	AT	AE1	Summary of Post-Treatment Adverse Events by System Organ Class and Preferred Term		SAC			
2.8.	AT	AE5	Summary of Post-Treatment Adverse Events by Maximum Intensity by System Organ Class and Preferred Term	ICH E3 Add a Total column across all severities	SAC			
2.9.	AT	AE3	Summary of Common (>=3%) On-Treatment Adverse Events by Overall Frequency	ICH E3 ≥3% (prior to rounding to nearest percent)	SAC			
2.10.	AT	SHELL	Summary of Exposure Adjusted On-Treatment Common (>=3%) Adverse Events by System Organ Class and Preferred Term	≥3% (prior to rounding to nearest percent)	SAC			
2.11.	AT	AE1	Summary of On-Treatment Drug-Related Adverse Events by System Organ Class and Preferred Term	ICH E3	SAC			
2.12.	AT	SHELL	Summary of Exposure Adjusted On-Treatment Drug-Related Adverse Events by System Organ Class and Preferred Term		SAC			
2.13.	AT	AE5	Summary of On-Treatment Drug-Related Adverse Events by System Organ Class and Preferred Term and Maximum Intensity	Add a Total column across all severities	SAC			
2.14.	AT	AE1	Summary of Adverse Events Reported on Day of Dosing by System Organ Class and Preferred Term		SAC			
2.15.	AT	SHELL	Summary of On-Treatment Adverse Events by Age Group (12- 17, 18-64, >=65 years)		SAC			
2.16.	AT	SHELL	Summary of On-Treatment Adverse Events by Highest Anti Drug Antibody Result At Any Time Post Baseline		SAC			
2.17.	AT	SHELL	Summary of Post-Treatment Adverse Events by Highest Anti Drug Antibody Result At Any Time Post Baseline		SAC			

Safety: Tables							
No.	Population	IDSL / Example Shell	Title	Programming Notes	Deliverable		
2.18.	AT	AE15	Summary of Common (>=3%) Non-serious Adverse Events by System Organ Class and Preferred Term (Number of Subjects and Occurrences)	FDAAA, EudraCT ≥3% (prior to rounding to nearest percent)	SAC		
Serious	and Other Sig	nificant Adverse	Events				
2.19.	AT	AE1	Summary of Pre-Treatment Serious Adverse Events by System Organ Class and Preferred Term		SAC		
2.20.	AT	AE1	Summary of On-Treatment Serious Adverse Events by System Organ Class and Preferred Term		SAC		
2.21.	AT	AE1	Summary of Post-Treatment Serious Adverse Events by System Organ Class and Preferred Term		SAC		
2.22.	AT	SHELL	Summary of Exposure Adjusted On-Treatment Serious Adverse Events by System Organ Class and Preferred Term		SAC		
2.23.	AT	SHELL	Summary of On-Treatment Serious Adverse Events by Age Group (12-17, 18-64, >=65 years)		SAC		
2.24.	AT	AE1	Summary of Fatal Serious Adverse Events		SAC		
2.25.	AT	SHELL	Summary of Fatal Serious Adverse Events by Age Group (12- 17, 18-64, >=65 years)		SAC		
2.26.	AT	AE1	Summary of Non-Fatal Serious On-Treatment Adverse Events by System Organ Class and Preferred Term		SAC		
2.27.	AT	AE1	Summary of Non-Fatal Serious Post-Treatment Adverse Events by System Organ Class and Preferred Term		SAC		
2.28.	AT	SHELL	Summary of Exposure Adjusted On-Treatment Non-Fatal Serious Adverse Events by System Organ Class and Preferred Term		SAC		

Safety:	Safety: Tables							
No.	Population	IDSL / Example Shell	Title	Programming Notes	Deliverable			
2.29.	AT	AE1	Summary of Drug-Related Fatal Serious Adverse Events by System Organ Class and Preferred Term		SAC			
2.30.	AT	AE5	Summary of Drug-Related Serious Adverse Events by System Organ Class and Preferred Term and Maximum Intensity	Add a Total column across all severities	SAC			
2.31.	AT	AE3	Summary of Adverse Events Leading to Permanent Discontinuation of Study Treatment or Withdrawal from Study by System Organ Class and Preferred Term /by Overall Frequency	IDSL	SAC			
2.32.	AT	SHELL	Summary of Exposure Adjusted On-Treatment Adverse Events Leading to Permanent Discontinuation of Study Treatment or Withdrawal from Study by System Organ Class and Preferred Term		SAC			
2.33.	AT	AE16	Summary of On-Treatment Serious Adverse Events by System Organ Class and Preferred Term (Number of Subjects and Occurrences)	FDAAA, EudraCT	SAC			
Advers	e Events of Sp	ecial Interest						
2.34.	AT	AE1	Summary of On-Treatment Adverse Events Meeting Anaphylaxis Criteria	Present by Anaphylactic Criterion 1, 2 and 3 rather than SOC as shown in AE1 Insert footnote: "Events displayed are a subset of reactions defined by the Investigator as being systemic"	SAC			
2.35.	AT	SHELL	Summary Profile of On-Treatment Adverse Events Meeting Anaphylaxis Criteria	Insert footnote: "Events displayed are a subset of reactions defined by the Investigator as being systemic"	SAC			
2.36.	AT	AE1	Summary of On-Treatment Adverse Events Defined by the Investigator as Being Systemic (non-allergic or allergic/hypersensitivity) Reactions		SAC			

Safety: Tables						
No.	Population	IDSL / Example Shell	Title	Programming Notes	Deliverable	
2.37.	AT	SHELL	Summary Profile of On-Treatment Systemic (non-allergic or allergic/hypersensitivity) Reactions		SAC	
2.38.	AT	SHELL	Summary Profile of On-Treatment Systemic Allergic Reactions		SAC	
2.39.	AT	SHELL	Summary Profile of On-Treatment Systemic Non-Allergic Reactions		SAC	
2.40.	AT	AE1	Summary of On-Treatment Adverse Events Defined by the Investigator as being Local Injection Site Reactions		SAC	
2.41.	AT	SHELL	Summary Profile of On-Treatment Local Injection Site Reactions		SAC	
2.42.	AT	AE1	Summary of On-Treatment Opportunistic Infections		SAC	
2.43.	AT	SHELL	Summary Profile of On-Treatment Opportunistic Infections		SAC	
2.44.	AT	AE1	Summary of On-Treatment Malignancies		SAC	
2.45.	AT	SHELL	Summary Profile of On-Treatment Malignancies		SAC	
2.46.	AT	AE1	Summary of On-Treatment Serious Cardiac, Vascular and Thromboembolic Adverse Events		SAC	
2.47.	AT	SHELL	Summary Profile of On-Treatment Serious Cardiac, Vascular and Thromboembolic Adverse Events		SAC	
2.48.	AT	AE1	Summary of On-Treatment Serious Ischemic Adverse Events		SAC	
2.49.	AT	SHELL	Summary Profile of Serious Ischemic Adverse Events		SAC	
2.50.	AT	SHELL	Summary of Serious Adverse Events and Adverse Events of Special Interest		SAC	
Cardio	vascular Events	S				
2.51.	AT	SHELL	Summary of All Cause Deaths and Cardiovascular Events Reported by the Investigator		SAC	

Safety: Tables							
No.	Population	IDSL / Example Shell	Title	Programming Notes	Deliverable		
2.52.	AT	SHELL	Summary of CEC Adjudicated All Cause Deaths and Cardiovascular Events of Interest		SAC		
Labora	tory: Chemistry	/					
2.53.	AT	LB1	Summary of Chemistry Changes from Baseline	ICH E3 Includes Baseline values.	SAC		
2.54.	AT	LB3	Summary of Chemistry Results (Changes from Baseline Relative to the Normal Range)	See also format of Safety Table 7.36 (MEA115588 'final reporting effort)	SAC		
2.55.	AT	LB3	Summary of Chemistry Results (Changes from Baseline Relative to the Reference Range [Potential Clinical Importance])	See also format of Safety Table 7.36 (MEA115588 'final reporting effort)	SAC		
Labora	tory: Haematol	ogy					
2.56.	AT	LB1	Summary of Haematology Changes from Baseline	ICH E3 Includes baseline values.	SAC		
2.57.	AT	LB3	Summary of Haematology Results (Changes from Baseline Relative to the Normal Range)	See also format of Safety Table 7.42 (MEA115588 'final reporting effort)	SAC		
2.58.	AT	LB3	Summary of Haematology Results (Changes from Baseline Relative to the Reference Range [Potential Clinical Importance])	See also format of Safety Table 7.42 (MEA115588 'final reporting effort)	SAC		
Labora	tory: Hepatobil	iary (Liver)		•			
2.59.	AT	LIVER10	Summary of Subjects Meeting Emergent Hepatobiliary Laboratory Abnormality Criteria	IDSL	SAC		
ECG	·						
2.60.	AT	EG1	Summary of ECG Findings	IDSL	SAC		
2.61.	AT	EG2	Summary of Change from Baseline in ECG Values by Visit	Includes baseline values.	SAC		
2.62.	AT	SHELL	Summary of Actual and Change From Baseline QTc(F) Values by Category (msec)		SAC		

Safety:	Safety: Tables								
No.	Population	IDSL / Example Shell	Title	Programming Notes	Deliverable				
2.63.	AT	SHELL	Summary of Actual and Change From Baseline QTc(B) Values by Category (msec)		SAC				
Vital Si	gns								
2.64.	AT	VS1	Summary of Change from Baseline in Vital Signs	ICH E3 Includes Baseline values.	SAC				
Immun	ogenicity								
2.65.	AT	SHELL	Summary of ADA Assay Results	See format of Other Assessments Table 8.01 (MEA115588 'final' reporting effort)	SAC				
2.66.	AT	SHELL	Summary of Treatment Emergent ADA Assay Results		SAC				
2.67.	AT	SHELL	Summary of NAb Assay Results	See format of Other Assessments Table 8.02 (MEA115588 'final' reporting effort)	SAC				

